10.4.2.1 Adverse Events

For analysis purpose, AEs will be classified as pretreatment AEs, TEAEs, or post-treatment AEs, defined as follows:

- **Pretreatment AE:** any AE that occurred before the first dose date of study drug in the OLE Safety Period.
- **TEAE:** any AE that worsened (either in severity or seriousness) or that was newly developed at or after the first dose date of study drug through the end of the OLE Safety Period.
- **Post-treatment AE:** any AE that worsened (either in severity or seriousness) or that was newly developed after the OLE Safety Period.

For AEs with completely missing or partially missing start dates, if there is no clear evidence that the AEs were pretreatment or post-treatment, the AEs will be classified as TEAEs.

Details for imputing missing or partial start dates of adverse events are defined in Appendix D.

An overview of all TEAEs during OLE Safety Period will be provided with the following categories:

- Number of TEAEs (total number of TEAEs only)

- Subjects with any TEAEs
- Subjects with TEAEs by strongest relationship
- Subjects with TEAEs by maximum severity
- Subjects with TEAEs leading to study drug discontinuation (discontinuation of any study drug)
- Subjects with TEAEs leading to study drug interruption (interruption of any study drug)
- Subjects with grade 3/4 TEAEs
- Subjects with related TEAEs
- Subjects with serious TEAEs
- Subjects with related serious TEAEs
- Subjects with TEAEs leading to death

The frequency counts and percentages as well as the exposure adjusted event rate will be presented for the above overview table. The exposure adjusted rate will not be presented for strongest relationship and maximum severity categories.

The following summary tables of TEAEs during OLE Safety Period will be presented:

- All TEAEs
- TEAEs leading to treatment discontinuation
- TEAEs leading to treatment interruption
- Serious TEAEs
- TEAEs leading to death
- Grade 3/4 TEAEs
- TEAEs by strongest relationship
- TEAEs by maximum severity
- Related TEAEs
- Related serious TEAEs

Summaries will be presented by MedDRA SOC and PT using frequency counts and percentages (i.e., number and percentage of subjects with an event) and the exposure adjusted event rate (except for summary by strongest relationship and maximum severity). When summarizing the number and percentage of subjects, subjects with multiple occurrences of the same AE or a continuing AE will be counted once and only the maximum severity level will be presented in the severity summaries, and the strongest relationship level will be presented in the relationship summaries.

Additional summary table in which the frequency counts and percentages as well as the exposure adjusted event rate will be presented for TEAEs during the OLE Safety Period:

- All TEAEs by PT

All AEs, including pretreatment AEs, TEAEs, and post-treatment AEs, will be presented in an individual subject data listing based on the OLE All Subjects Set. In addition, a listing containing individual subject adverse event data for TEAEs leading to treatment discontinuation, TEAEs leading to treatment interruption, Grade 3/4 TEAEs, SAEs and all deaths will be provided separately, with a flag indicating the TEAE status for SAEs and deaths.

10.4.2.2 Clinical Laboratory

For the treatment-emergent laboratory assessments, the observed values and change from baseline values of the continuous hematology, coagulation and chemistry results will be summarized in SI units at each visit during the OLE Safety Period.

The number and percentage of subjects with selected test values meeting at least 1 threshold analysis criterion event during the OLE Safety Period will be summarized. The threshold analysis criterion shift from baseline will also be summarized for selected laboratory parameters. The threshold analysis criteria are provided in Appendix E.

For selected LFT laboratory tests (alanine transaminase [ALT], aspartate transaminase [AST], alkaline phosphatase [ALP], and total bilirubin), a scatter plot of the maximum treatment-emergent value versus the baseline value corresponding to \times ULN (upper limit of normal) will be presented. Further, a scatter plot of the maximum treatment-emergent value of ALT and AST, separately, versus the maximum treatment-emergent value of total bilirubin corresponding to \times ULN will also be presented.

Results of urinalysis and the positive urine/serum pregnancy test will be listed in individual subject data listings only. For positive serum pregnancy listing, subjects with serum HCG which elevated above the upper limit of normal will be selected.

In addition, a listing containing individual subject hematology, chemistry, and coagulation values will be provided. This listing will include data from both scheduled and unscheduled visits.

10.4.2.3 Electrocardiogram

For the following ECG measurements during the OLE Safety Period, a summary of observed values and change from baseline values will be provided at each visit for the following ECG measurements (in msec): RR interval, PR interval, QT interval, QTcF interval, QRS duration, and Heart Rate (beats per minute).

The number and percentage of subjects meeting at least 1 threshold analysis criterion during the OLE Safety Period will be summarized. The threshold analysis criteria are provided in Appendix E.

In addition, a listing containing individual subject ECG values will be provided. This listing will include data from both scheduled and unscheduled visits.

10.4.2.4 Vital Signs

For the vital signs measurements during the OLE Safety Period, the observed values and change from baseline values will be summarized at each visit. The following vital signs parameters will be summarized: systolic and diastolic blood pressure (mm Hg), body temperature (°C), pulse rate (beats per minute), and respiratory rate (breaths per minute).

The number and percentage of subjects meeting at least 1 threshold analysis criterion during the OLE Safety Period will be summarized. The threshold analysis criteria are provided in Appendix E.

In addition, a listing containing individual subject vital sign values will be provided. This listing will include data from both scheduled and unscheduled visits.

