^b If a subject prematurely discontinues study drug treatment, an ETT Visit should be scheduled as soon as possible after the decision to discontinue treatment (Section 9.1.3).

^c The Safety Follow-up Visit is required for all subjects unless otherwise specified. If an ETT Visit occurs 3 weeks or later following the last dose of study drug, then the ETT Visit replaces the Safety Follow-up Visit (Section 9.1.2).

^d The Day 1 Visit should be on the same day as the last scheduled visit of the parent study (Section 9.1.1). Subjects whose Day 1 Visit is NOT within 1 day of the last scheduled visit of the parent study will repeat all Day 1 assessments. Subjects whose Day 1 Visit is within 1 day of the last scheduled visit of the parent study will NOT have to repeat any Day 1 assessments that were specified to be performed at the last scheduled visit in the parent study.

Table 3-1 Study VX19-445-107: Part A Treatment Period and Safety Follow-up Visit

Event/Assessment ^a	Part A Treatment Period (96 weeks)						Part A ETT Visit ^b	Part A Safety Follow-up Visit ^c (28 ± 7 Days After Last Dose of Study Drug)	Comments
	Day 1 ^d	Weeks 8, 16, 24, 36 (± 5 Days)	Weeks 4, 12, 20, 28, 32, 40, 44, 52, 56, 64, 68, 76, 80, 88, 92 (± 5 Days)	Week 48 (± 5 Days)	Weeks 60, 72, 84 (± 5 Days)	Week 96 ^e (± 5 Days)			
Vital signs	X	X		X	X	X	X	X	Performed after subject has been at rest (seated or supine) for at least 5 minutes (Section 11.5.3).
Pulse oximetry	X	X		X	X	X	X	X	Performed after subject has been at rest for at least 5 minutes (Section 11.5.3).
Standard 12-lead ECG	X	Week 24		X	Week 72	X	X	X	Performed after subject has been at rest for at least 5 minutes (Section 11.5.4).
Spirometry	X	X		X	X	X	X	X	Should be performed pre-bronchodilator at approximately the same time at each visit (Section 11.3.1).
Sweat chloride	X	Week 24		X	Week 72	X	X		At each time point, 2 samples will be collected (1 sample from each arm; Section 11.3.2).
Pregnancy test (all female subjects)	urine	urine	urine	urine	urine	serum	serum	serum	At telephone contact visits, a urine pregnancy test will be performed with a home kit provided by the study site (Section 11.5.2).
Serum chemistry	X	X		X	X	X	X	X	Section 11.5.2
Hematology	X	X		X	X	X	X	X	Section 11.5.2
Coagulation	X	Week 24		X	Week 72	X	X	X	Section 11.5.2
Urinalysis	X			X		X	X		Section 11.5.2
Multiple breath washout	X	Week 24		X	Week 72	X	X		Performed in multiple replicates, pre-bronchodilator, and before the spirometry assessment (Section 11.3.3).

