AE: adverse event; BMI: body mass index; CF: cystic fibrosis; CFQ-R: Cystic Fibrosis Questionnaire-Revised; ETT: Early Termination of Treatment; FE-1: fecal elastase-1; ICF: informed consent form; IRT: immunoreactive trypsinogen; PEx: pulmonary exacerbation; SAE: serious adverse event

Table 3-2 Study VX19-445-107: Part B Treatment Period and Safety Follow-up Visit

Event/Assessment ^a	Part B Treatment Period (96 weeks)					Part B ETT Visit ^b	Part B Safety Follow-up Visit ^c (28 ± 7 Days After Last Dose of Study Drug)	Comments
	Day 1 ^d	Weeks 4, 8, 16, 20, 28, 32, 40, 44, 52, 56, 64, 68, 76, 80, 88, 92 (± 5 Days)	Weeks 12, 36, 60, 84 (± 5 Days)	Weeks 24, 48, 72 (± 5 Days)	Week 96 (± 5 Days)			
Clinic visit	X		X	X	X	X	X	
Telephone contact		X						When telephone contact takes the place of a clinic visit, a urine pregnancy test will be performed with a home kit provided by the study site (Section 11.5.2).
Part B Informed consent and assent	X							
Inclusion and exclusion criteria confirmation	X							See Section 8 for details.
CFQ-R	X			X	X	X	X	To be completed before any other assessments scheduled at relevant visits (Section 11.3.5).
Ophthalmologic examination					X	X		Subjects will have an ophthalmologic examination at Week 96 (Section 11.5.5). In addition, an ophthalmologic examination will be performed at the ETT Visit for subjects who discontinue study drug if the subject has received at least 12 weeks of study drug since their last ophthalmologic examination.
Full physical examination	X				X	X		Symptom-directed physical examinations will be performed at any time if deemed necessary by the investigator or healthcare provider (Section 11.5.3).
Weight, height, and BMI	X		X	X	X	X	X	Weight and height measured with shoes off (Section 11.3.4).
Vital signs	X		X	X	X	X	X	Performed after subject has been at rest (seated or supine) for at least 5 minutes (Section 11.5.3).

^a All assessments will be performed before study drug dosing unless noted otherwise.

^b If a subject prematurely discontinues study drug treatment, an ETT Visit should be scheduled as soon as possible after the decision to discontinue treatment (Section 9.1.3).

^c The Safety Follow-up Visit is required for all subjects unless otherwise specified. If an ETT Visit occurs 3 weeks or later following the last dose of study drug, then the ETT Visit replaces the Safety Follow-up Visit (Section 9.1.2).

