10 STATISTICAL ANALYSIS

10.1 General Considerations

The Schedule of Assessments is provided in Section 3 of the CSP. The precision standards for reporting safety and efficacy variables are provided in an internal Biometrics document that specifies the programming rules including the precision for derived variables.

Continuous variables will be summarized using the following descriptive summary statistics: the number of subjects (n), mean, standard deviation (SD), median, minimum value (min), and maximum value (max).

Categorical variables will be summarized using counts and percentages. Percentages will be presented to 1 decimal place.

Baseline unless otherwise specified, is defined as the most recent non-missing measurement (scheduled or unscheduled) collected prior to the first dose of study drug in the parent study.

Note: for subjects who take Orkambi or Symdeko (branded as Symkevi in Europe) during the 28 days before the screening visit, the data collected at screening visit will not be used for baseline derivation for spirometry, sweat chloride and LCI.

Absolute change from baseline will be calculated as Post-baseline value – Baseline value.

Relative change from baseline will be calculated and expressed in percentage as $100\% \times (\text{Post-baseline value} - \text{Baseline value}) / \text{Baseline value}$.

Unscheduled visits: Unscheduled visit measurements will be included in analysis as follows:

- In scheduled visit windows per specified visit windowing rules
- In the derivation of baseline and last on-treatment measurements
- In the derivation of maximum and minimum values during TE period, and maximum and minimum change from baseline values during TE period for safety analyses
- In individual subject data listings as appropriate

Visit windowing rules: The analysis visit windows for protocol-defined visits are provided in Appendix A.

Incomplete/missing data will not be imputed, unless specified otherwise.

Outliers: No formal statistical analyses will be performed to detect or remedy the presence of statistical outliers, unless specified otherwise.

Multiplicity: There will be no multiplicity adjustment as no hypothesis test is planned for safety analysis, unless specified otherwise.

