10.4.1.4 Vital Signs

For the vital signs measurements during the OLE Safety Period for Part A, the observed values and change from baseline values will be summarized at each visit. The following vital signs parameters will be summarized: systolic and diastolic blood pressure (mm Hg), body temperature (°C), pulse rate (beats per minute), and respiratory rate (breaths per minute).

The number and percentage of subjects meeting at least 1 threshold analysis criterion during the OLE Safety Period for Part A will be summarized. The threshold analysis criteria are provided in Appendix E.

In addition, a listing containing individual subject vital sign values will be provided. This listing will include data from both scheduled and unscheduled visits.

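### The SBP and DBP threshold counts have an unknown, potentially high rate under no drug effect, so they cannot be read as treatment-emergent

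*SAP*

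**What the plan says.** For the pooled study, SAP 10.4.2.4 plans: "The number and percentage of subjects meeting at least 1 threshold analysis criterion during the OLE Safety Period will be summarized". SAP 10.4.1.4 has the matching rule for Part A: "The number and percentage of subjects meeting at least 1 threshold analysis criterion during the OLE Safety Period for Part A will be summarized".

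The criteria are in Appendix E, Table 13-7: SBP above 120 or below 70 mmHg, DBP above 80 or below 50 mmHg, and weight gain or loss of at least 5% from baseline. The weight rows refer to baseline. The four pressure rows do not, and they carry no age, sex, height or confirmation condition. SAP 10.1 brings in unscheduled measurements: "In the derivation of maximum and minimum values during TE period". Baseline itself is the last value "collected prior to the first dose of study drug in the parent study".

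Other safety sections do use pre-treatment status. SAP 10.4.2.2 says of laboratory tests: "The threshold analysis criterion shift from baseline will also be summarized for selected laboratory parameters". SAP 10.4.2.5 plans a shift from baseline to the lowest oxygen saturation. In Table 13-6 the PR criterion requires an increase from baseline, and QTc has increase-from-baseline rows. SAP 10.4.2.4 plans no shift for blood pressure, but it does plan observed values and change from baseline at each visit, and a listing. Safety analysis is descriptive only (SAP 10.4.2), and no expected threshold rate is stated.

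**The concern.** Vital signs are a named component of the primary endpoint (Protocol 7.1, SAP 6.1). The threshold percentage is the part of the vital-signs section that speaks to individual children rather than means. As written, it mixes four things: pressure already beyond a limit before treatment, growth over nearly four years, isolated readings among many, and any drug effect. Only the last is of interest, and with one arm there is nothing to subtract.

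The percentage also grows with the length of observation. The Part A table and the pooled table differ in number of visits and in the children's age, so a larger pooled figure could be mistaken for worsening on longer treatment. The AE tables carry exposure-adjusted rates (SAP 10.4.2.1); this table does not. The by-visit changes do not settle the matter, because they also contain growth since the parent-study baseline.

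**Working it through.** The plan states no expected rate, so there is no figure of its own to reproduce.

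**Visits (Protocol Tables 3-1 and 3-2, vital-signs row, after Day 1).** Part A: Weeks 8, 16, 24, 36, 48, 60, 72, 84, 96 = 9. Part B: Weeks 12, 24, 36, 48, 60, 72, 84, 96 = 8. Total 17, before follow-up, early-termination and unscheduled readings.

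**Independent-visit bound.** If a single visit is beyond a limit with probability p, the chance of at least one in 17 is 1 − (1 − p)^17. For p = 2%, 4%, 5% and 10% this gives 29%, 50%, 58% and 83%.

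**Correlated visits with growth, no drug effect.** Everything in this step is an assumption. Each pressure is a mean, plus a linear yearly drift, plus a subject effect and visit noise (both normal). The SBP–DBP correlation is 0.5. Readings are unrounded; rounding to whole mmHg lowers the figures by up to a few points. The last two columns add a true 5 mmHg to both SBP and DBP on treatment.

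| Set | SBP mean/SD | DBP mean/SD | Within-subject correlation | Drift per year, SBP/DBP | Any of four rows | SBP >120 | Any, +5 | SBP >120, +5 |
|---|---|---|---|---|---|---|---|---|
| Lowest | 96/7.5 | 64/6 | 0.6 | 1/0.3 | 13% | 2% | 29% | 10% |
| Central, high correlation | 102/9 | 62/7.5 | 0.7 | 1.5/0.5 | 46% | 23% | 58% | 46% |
| Central | 102/9 | 62/7.5 | 0.5 | 1.5/0.5 | 60% | 32% | 72% | 58% |
| Central, low correlation | 102/9 | 62/7.5 | 0.35 | 1.5/0.5 | 69% | 38% | 81% | 68% |
| Highest | 104/10 | 64/8 | 0.4 | 2/0.7 | 81% | 61% | 91% | 83% |

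**Wider inputs.** A second grid of 27 sets used mean SBP 100 to 106 at age 9 rising 1.75 mmHg per year, mean DBP 58 to 64 rising 0.7, SBP between- and within-subject SDs of 6 to 8 each, and DBP SDs of 4 to 5 (between) and 6 to 7 (within). It gave 52% to 92% for any row and 25% to 70% for SBP above 120. Over both grids the range is therefore 13% to 92% for any row and 2% to 70% for SBP above 120.

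**What drives the central figure.**
- Visits: any row is 41% with the 9 Part A visits and 60% with 17.
- Growth: over 17 visits SBP above 120 is 18% without drift and 32% with it.
- Pre-treatment status: 8% already meet one of the four rows at a single baseline reading (5% to 26% in the 27-set grid).

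**Precision.** With 64 subjects enrolled (SAP 7.2), the 95% half-width at 60% is 1.96 × √(0.6 × 0.4 / 64) = 12 points. That equals the 72% − 60% = 12-point movement of the combined figure under the 5 mmHg shift.

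**The case against.** Two stronger readings are tempting, and neither is supported. The first is that most subjects will be flagged with no drug effect. That rests on a blood-pressure distribution the documents do not give. It holds for the four rows combined in the central and higher sets, fails in the lower or highly correlated ones, and often fails for a single row.

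The second is that the table cannot show a blood-pressure signal. The combined figure is blunt because low-side rows offset high-side rows, but the SAP does not clearly plan a four-row blood-pressure composite. Read literally, meeting at least one criterion would also include the weight rows. Read by row, SBP above 120 moves from 32% to 58% in the central set with a true 5 mmHg rise, which is visible.

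Other points stand. Excluding children above 120 at baseline changes that row little: 25% to 70% becomes 24% to 62% in the 27-set grid. Protocol 13.1.1.2 requires clinically significant worsening of vital signs from baseline to be recorded as an AE, and SAP 10.4.2.1 tabulates AEs, so this table is not the only categorical route. Threshold counts are descriptive screens read with listings. A rule requiring two consecutive visits, typically 12 weeks apart, would hide transient changes.

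These points limit the claim but do not answer it. When the rate expected under no effect could lie almost anywhere in a wide range, an observed 40% or 60% has no reference value.

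**Conclusion.** The pressure rows count any single on-treatment reading beyond a fixed limit in growing children, whatever their status before treatment. The rate under no drug effect is therefore unknown, potentially high, and dependent on the number of visits and on growth: about 2% to 70% for SBP above 120 and about 13% to 92% for any of the four rows. In a single-arm study these percentages cannot be read as treatment-emergent.

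The ranges depend wholly on assumed means, SDs, correlations and drift. The structural facts do not: 17 scheduled visits, fixed limits, and no baseline, age or repeat condition. A reader might infer that most subjects will be flagged, or that no signal could be seen; the documents establish neither. The defect is one of interpretation in one descriptive table of a primary-endpoint component, with other blood-pressure outputs alongside it.

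**What to change.** In SAP 10.4.1.4, SAP 10.4.2.4 and Table 13-7:

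1. Report each SBP and DBP row separately, with a shift from baseline to the worst post-baseline value. Alternatively, count only subjects not beyond the limit at the parent-study baseline. Shifts from baseline are already planned for laboratory parameters and pulse oximetry.
2. Use percentile limits specific to age, sex and height from a named paediatric reference. Keep the present fixed rows as a supplement, each beside the percentage meeting it at baseline.
3. Optionally add a supplementary row for subjects beyond the limit at two consecutive visits. It should not replace the any-reading count.

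The steps do different work. Percentile limits remove growth, and the shift shows prior status. Neither removes the many-visits effect: a limit exceeded 5% of the time at each visit still gives up to 58% over 17 independent visits. The two-visit row addresses that. For high SBP, an age-specific 95th percentile limit, new since baseline and met at two consecutive visits, gave about 5% to 6% under no effect and 16% to 25% with a true 5 mmHg rise. This assumes that the reference fits the population; DBP and low-side limits were not examined.

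The cost is SAP wording, the choice of a reference and one reprogrammed table. Age, sex, height and baseline pressure are already collected.

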10.4.2.5 Pulse Oximetry

For the percent of oxygen saturation measurements using pulse oximetry during the OLE Safety Period, a summary of observed values and change from baseline values will be provided at each visit.

The number and percentage of subjects with shift change from baseline (normal/missing and low according to the reference range) to the lowest percent of oxygen saturation during the OLE Safety Period will be summarized. The reference range for normal oxygen saturation is specified as >95%, and <=95% for low oxygen saturation.

10.4.2.6 Ophthalmologic Examinations

The ophthalmologic examination results will be presented in individual subject data listings.

10.4.2.7 Physical Examination

No tables/figures/listings will be provided for PE data.

10.4.2.8 COVID-19 Impacted Visits

A listing containing subjects' visits impacted due to COVID-19 will be provided.

10.4.2.9 Supportive Safety Analysis

10.4.2.9.1 Adverse Events of Special Interest

For this study, elevated transaminases events and rash events, as determined by MedDRA Preferred Terms in the respective Customized MedDRA Queries (CMQ), are considered as adverse events of special interest.

For treatment-emergent elevated transaminases events and rash events, the following categories will be summarized:

- Subjects with events
- Subjects with events by maximum severity
- Subjects with events leading to treatment discontinuation
- Subjects with events leading to treatment interruption
- Subjects with serious events
- Subjects with related serious events
- Subjects with events leading to death
- Duration of events
- Time-to-onset of first event (with the first dose date of study drug in the OLE study as the reference while calculating time-to-onset)

In addition, for treatment-emergent rash events, the above categories will be summarized for the following subgroups:

- Sex (male, female)

